### 6.2.2. Unscheduled Visits

Should it become necessary to repeat an evaluation (eg, laboratory tests), the results of the repeat evaluation should be entered as appropriate in an additional unscheduled visit page of the eCRF.

[figure not shown]
### 6.2.3. End of Treatment

An EOT evaluation will be performed for subjects who are withdrawn from study treatment for any reason as soon as possible after the decision to permanently discontinue study treatment has been made. An administrative window of  $\pm 7$  days is permitted for the EOT Visit, unless noted otherwise. If a subject is discontinued during a regularly-scheduled visit, all EOT evaluations should be completed at that visit.

The following evaluations will be performed as specified in the Table of Events ([Table 4](#)). For each evaluation, the same parameters as required at screening or on Day 1 of Cycle 1 should be evaluated.

- Registration of treatment discontinuation in IWRS
- HRQoL outcomes (EORTC QLQ-C30 and EQ-ED-5L questionnaires)
- Study drug accountability (where applicable; refer to [Section 7.5](#))
- Study drug dispensing and administration (where applicable; refer to [Section 7](#))
- ECOG performance status

- Physical examination, vital signs, and body weight. Significant findings are to be reported on the appropriate eCRF page.
- The following laboratory assessments will be done locally:
  - ECHO or MUGA scan if clinically indicated
  - 12-lead ECG
  - A serum or urine (investigator’s discretion under local regulations)  $\beta$ -hCG pregnancy test (sensitivity of at least 25 mIU/mL) (for FBCPs only)
- The following laboratory assessments will be done centrally:
  - Urinalysis and/or coagulation test if clinically indicated
  - Hematology panel
  - Chemistry panel
  - Cardiac markers (not necessary for the EOT Visit if it was last performed within 14 days)
  - Fasting lipid panel (not necessary for the EOT Visit if it was last performed within 28 days)
- Evaluations of AEs, [REDACTED] concomitant medications, concomitant procedures, and transfusions (monitored through 28 days after the last study treatment)
- Clinical site staff should confirm if any transfusions were received by the subject (including any at outside local institutions in between study visits) prior to each IP administration via use of patient diary or other local procedure in place at the investigational site.
- Bone marrow aspirate and/or biopsy, peripheral blood smear and, if applicable, local cytogenetics, for response assessment (not necessary for the EOT Visit if it was last performed within 28 days)
- Response to treatment, per modified IWG, and HI will be assessed if bone marrow samples are collected for assessing response at the EOT Visit (see above)
- Bone marrow aspirate sampling for pharmacodynamic assessments will be performed in all subjects if bone marrow samples are collected for assessing response at the EOT Visit (see above) and if sufficient bone marrow material remains

- Peripheral blood sampling for pharmacodynamic assessments will be performed in all subjects.

### 6.3. Follow-up Period

All subjects discontinued from study treatment for any reason other than withdrawal of consent for follow-up will continue to have the following assessments in the Follow-up Period every 28 days performed by site visits or phone calls:

- AEs, [REDACTED] concomitant medication, concomitant procedures and transfusions for 28 days after the last study treatment.
  - Thereafter, SAEs made known to the investigator at any time that are suspected of being related to study treatment should be managed as described in Section 10.1.
- Clinical site staff should confirm if any transfusions were received by the subject (including any at outside local institutions in between study visits) prior to each IP administration via use of patient diary or other local procedure in place at the investigational site.
- Survival follow-up every 4 weeks ( $\pm$  7 days) until death, lost to follow-up, withdrawal of consent for further data collection, or the End of Trial, whichever occurs first. Information on subsequent AML therapies should be collected at the same schedule as survival follow-up. Survival follow-up may be conducted by record review (including public records) and/or telephone contact with the subject, family, or the subject's treating physician where allowed by local regulations.
- Females of childbearing potential should avoid becoming pregnant for 4 months after the last study treatment, and male subjects should avoid fathering a child for 4 months after the last study treatment (6 months after the last dose of azacitidine in Canada).

Subjects who discontinue study treatment prior to relapse, progression, or the start of second line therapy will continue to have the following assessments in the Follow-up period every 28 days performed by site visits until confirmation of relapse or progression, or until they have died, or are lost to follow up, or withdrew consent for further data collection, or study closure.

- AEs, [REDACTED] concomitant medication, concomitant procedures and transfusions for 28 days after the last study treatment.

- Thereafter, SAEs made known to the investigator at any time that are suspected of being related to study treatment should be managed as described in Section 10.1.
- Clinical site staff should confirm if any transfusions were received by the subject (including any at outside local institutions in between study visits) prior to each IP administration via use of patient diary or other local procedure in place at the investigational site.
- Survival follow-up every 4 weeks ( $\pm 7$  days) until death, lost to follow-up, withdrawal of consent for further data collection, or the End of Trial, whichever occurs first. Information on subsequent AML therapies should be collected at the same schedule as survival follow-up. Survival follow-up may be conducted by record review (including public records) and/or telephone contact with the subject, family, or the subject's treating physician where allowed by local regulations.
- Females of childbearing potential should avoid becoming pregnant for 4 months after the last study treatment, and male subjects should avoid fathering a child for 4 months after the last study treatment (6 months after the last dose of azacitidine in Canada).
- Bone marrow aspirate and/or biopsy, peripheral blood smear and, if applicable, local cytogenetics report, must be available for local review for assessing response or disease diagnosis, every 8 weeks ( $\pm 28$  days). In addition, ensure peripheral blood for hematology is collected at the time of every bone marrow collection.
- Response to treatment, per modified IWG, and HI will be assessed if bone marrow samples are collected for assessing response in subjects who discontinue study treatment prior to relapse or progression.

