**Table 4: Table of Events (Continued)**

Events Table covers both Phase 1b & 2 (unless otherwise noted)	Screening Period	Treatment Period a							Follow-up Period a	
	Screening	28-day cycles							EOT b	Follow-up
		Cycles 1 to 2				Cycles 3 to 4		Cycle 5 and beyond		
		Days -28 to -1	Day 1	Day 8	Day 15	Day 22	Day 1	Day 15		
Concomitant Medications and Procedures	Continuous until 28 days after the last study treatment									
Transfusion Data Collection and Assessment†	Assess and record on an ongoing basis (prior to each dose of IP) until the next AML therapy after discontinuation from study treatment, death, lost to follow-up, withdrawal of consent for further data collection, or the End of Trial, whichever occurs first. Clinical site staff should confirm if any transfusions were received by the subject (including any at outside local institutions in between study visits) prior to each IP administration via use of patient diary or other local procedure in place at the investigational site.									
BMA for Disease Assessmentv, g	x	x w	-	-	-	x x	-	x y	x z	x p
Blood for Pharmacodynamicsg, v	x	x	-	x	-	x x	-	x y	x z	x p
BMBg, bb	x	x w	-	-	-	x x	-	x y	x z	x p
PB Smearg	x	x w	-	-	-	x x	-	x y	x z	x p
Cytogenetics Testingg	x	x w, cc	-	-	-	x x, cc	-	x y, cc	x z, cc	x p, cc
Modified IWG Response and HI	-	x w	-	-	-	x x	-	x y	x z	x p

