- p Whenever response/diagnosis is assessed in the Follow-up Period (ie, every 8 weeks [ $\pm$  28 days]). See Section 6.3 for details.
- q Day 1 ( $\pm$  14 days) of every 3rd cycle (eg, Cycles 3, 6, 9, etc) or more frequently per standard institutional practice. Not necessary for the EOT Visit if last performed within 14 days.
- r Day 1 ( $\pm$  28 days) of every 6th cycle (eg, Cycles 6, 12, 18, etc) or more frequently per standard institutional practice. Not necessary for the EOT Visit if last performed within 28 days.
- s Continuous starting after signing ICF through 28 days after the last study treatment. See Section 6.4.1 for details.
- t Including type, number of units, reasons, and date of transfusions taken  $\leq$  8 weeks prior to the start of study treatment through 28 days after the last study treatment. Thereafter, transfusions will continue to be collected until the next AML therapy after discontinuation from study treatment, death, lost to follow-up, withdrawal of consent for further data collection, or the End of Trial, whichever occurs first.
- v In addition to the frequency specified in the table, samples will also be collected if clinically indicated (eg, confirmation of CR/CRi/CRp, morphologic relapse after CR/CRi/CRp, or progression by a repeated bone marrow assessment at least 1 month later) or required for toxicity assessment. A sample of bone marrow and peripheral blood must also be sent at these time points for central pathology review.
- w Within 7 days prior to Day 1 of Cycle 2. The assessment is not required at Day 1 of Cycle 1.
- x Within 7 days prior to Day 1 of Cycle 3. The assessment is not required at Day 1 of Cycle 4.
- y Within 7 days prior to Day 1 of Cycle 5 and Day 1 of every 2nd cycle thereafter (eg, Cycles 7, 9, etc).
- z Not necessary for the EOT Visit if last performed within 28 days.
- bb A bone marrow biopsy can be collected in conjunction with an aspirate if it is standard institutional practice. A bone marrow biopsy must be collected if adequate aspirate is not attainable.
- cc A standard cytogenetic metaPhase preparation will be prepared if the bone marrow aspirate is obtained for assessing CR, morphologic relapse, or progressive disease and will be sent to the local laboratory for cytogenetic analysis.
- dd Including diary cards. See Section 7.6 for details.

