8.5. Prior/On-treatment/Follow-up Transfusions

Prior transfusions are defined as any type of transfusions received in 8 weeks (56 days) prior to the first dose date. On-treatment transfusions are defined as transfusions that are started on or after the start of study drug but before the last dose date + 28 days. Follow-up transfusions are defined as transfusions that are started on or after the last dose date + 28 days.

Subjects who received prior transfusions are considered transfusion dependent at baseline. The number of subjects receiving any transfusion product, and the number of subjects receiving any transfusion of particular type (RBCs, whole blood, platelets, plasma, other) will be summarized by dose cohort (Phase 1b) or treatment arm (Phase 2). On-treatment transfusions and follow-up transfusions will be summarized separately in tables.

In Phase 2, subjects who achieved post-baseline 56-day RBC transfusion independence, i.e., without RBC transfusion for at least 56 consecutive days post baseline during treatment exposure period, will be summarized by baseline RBC transfusion dependence status (Yes vs. No), within each category of best response (e.g., CR, CRi/CRp, PR/MLFS, SD, PD, etc.) and overall.

The post-baseline 56-day Platelet transfusion independence will be analyzed similarly.

For parameters RBC and Platelet in Phase 2, the number of subjects who are transfusion dependent at baseline, the changes from dependence to post baseline transfusion independence during treatment period will be summarized by treatment arm. The time to transfusion independence and duration of transfusion independence will be summarized by treatment arm as well. In addition, duration of transfusion independence will be summarized by with/without transfusion at baseline. For subjects which have multiple transfusion independent periods, time to the first transfusion independence period and duration of longest transfusion independence period will be summarized.

Transfusion type, number of units, reasons for taking transfusion, and dates of transfusions will be listed in a listing.

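### Protocol 6.2.3 and 6.3 stop transfusion collection 28 days after last treatment, Table 4 continues it to the next AML therapy, and the site prompt cannot work off treatment

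*Protocol*

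**What the plan says.** **Short window.** Protocol 6.2.3 lists transfusions at the end-of-treatment visit as "monitored through 28 days after the last study treatment". Protocol 6.3 limits collection to "concomitant medication, concomitant procedures and transfusions for 28 days after the last study treatment". It says so in the list for all discontinued subjects and again in the list for subjects still followed for response. The only item that 6.3 carries past the 28 days in that clause is treatment-related SAEs.

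**Long window.** The transfusion row of Table 4 reads "Assess and record on an ongoing basis (prior to each dose of IP) until the next AML therapy after discontinuation from study treatment", and then names death, loss to follow-up, withdrawal and End of Trial as the other stopping points. Footnote t covers the period to 28 days and adds: "Thereafter, transfusions will continue to be collected until the next AML therapy after discontinuation from study treatment". SAP 17.3 reproduces both. Protocol 3.1.1.8 and 3.1.2.4 list transfusions among the assessments that continue off treatment, without a time limit.

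**Site prompt.** In 6.3 staff are to confirm outside transfusions before each administration of investigational product. The Table 4 row uses the same trigger.

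**Use of the data.** For subjects off treatment without relapse or progression, 6.3 states: "Response to treatment, per modified IWG, and HI will be assessed if bone marrow samples are collected". Marrow is due every 8 weeks (± 28 days). CR needs at least 1 week without red-cell transfusion before each assessment (Appendix F). One HI-E criterion is an 8-week transfusion count (Appendix G), and 6.5.2 bases HI on transfusion records and local hematology. SAP 8.5 says: "Follow-up transfusions are defined as transfusions that are started on or after the last dose date + 28 days", and summarizes them separately from on-treatment transfusions.

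**The concern.** The two windows cannot both be followed, and the text that tells sites what to do after treatment carries the shorter one. The check meant to catch transfusions given elsewhere depends on a dosing visit that no longer occurs in follow-up.

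Two outputs are at stake. The follow-up transfusion summary in SAP 8.5 covers almost exactly the period that 6.3 leaves uncollected, so it would mix sites that record with sites that do not. Separately, a CR first documented at a follow-up marrow could have no recorded transfusion data behind its red-cell independence criterion. The same may hold for the HI-E transfusion count. CR rate and HI rate are named secondary endpoints of Phase 2.

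**Working it through.** The plan gives no figure on this point, so there is none to reproduce. The check is how much of each look-back falls inside the short window.

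**Inputs.** Last dose is day 0. Under 6.2.3 and 6.3 recording ends on day 28. The look-back L is 7 days for CR (Appendix F) and 56 days for the HI-E count (Appendix G). Follow-up marrow is every 8 weeks ± 28 days (6.3). The anchor of that interval is not stated. I assume it is the last dose, so the first follow-up marrow falls on days 28 to 84 and the second on days 84 to 140.

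**Formula.** For an assessment on day a ≥ 28, uncovered days = min(L, a − 28), and covered days = L − uncovered.

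| Assessment day | CR: covered of 7 | HI-E: covered of 56 |
|---|---|---|
| 28 | 7 | 56 |
| 29 | 6 | 55 |
| 35 | 0 | 49 |
| 56 (nominal first) | 0 | 28 |
| 84 | 0 | 0 |
| 112 (nominal second) | 0 | 0 |
| 140 | 0 | 0 |

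Only a first marrow at the earliest edge of its window is fully covered. The CR look-back is empty from day 35 and the HI-E look-back from day 84. Under footnote t the uncovered part is 0 days for both at every assessment before new AML therapy.

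**Could the gap alone produce an HI-E response?** Appendix G needs a fall of at least 4 units per 8 weeks. The documents give no transfusion rate, so take a constant need of r units per 8 weeks, all qualifying for the count, with r = 4, 6 and 8 as an illustrative range. Apparent fall = r × uncovered / 56.

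| r | Day 56 (28 uncovered) | Day 84 (56 uncovered) |
|---|---|---|
| 4 | 2 | 4 |
| 6 | 3 | 6 |
| 8 | 4 | 8 |

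At the nominal first marrow the gap reaches the threshold only if r is at least 4 × 56 / 28 = 8. When the whole window is uncollected, r of at least 4 is enough. This applies only if an off-treatment window counts. A note in Appendix G restricts the evaluation to red-cell transfusions given on treatment at a hemoglobin of 9.0 g/dL or less, whereas 6.3 has HI assessed off treatment. The two are not reconciled.

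**Which endpoints depend on it.**
- CR uses red-cell independence directly. CRi and CRp keep every CR criterion except one blood count, and PR needs the hematologic criteria of CR.
- MLFS has no transfusion criterion and counts in ORR (SAP 10.1). A subject with under 5% blasts who fails only transfusion independence can therefore still be a responder. A PR with blasts of 5% or more has no such fallback, which is why ORR is largely rather than wholly protected.
- Sponsor-derived CR is defined from laboratory data (SAP 10.2.10), and CRh has no transfusion criterion (SAP 10.2.11).
- Duration of response ends at relapse, progression or death (SAP 10.2.2), not at a transfusion.
- The 56-day transfusion-independence analysis in SAP 8.5 is confined to the treatment exposure period, which SAP 9.1 ends no later than 28 days after last dose. Even the short window covers it.

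**The case against.** Most of the text favors the longer window. Protocol 6.4 refers transfusion frequency to Table 4, and the list in 6.2.3 is itself introduced as following Table 4. Sections 3.1.1.8 and 3.1.2.4 set no limit, and SAP 8.5 expects later data. The 28-day clause groups transfusions with adverse events and concomitant medication, and the separate transfusion bullet in 6.3 has no 28-day limit. A site would have to follow one clause against all of this. That argument stands as evidence of intent and limits how often the gap is likely to occur. It does not remove the contradiction: 6.3 is the operative follow-up section, it states the short window twice, and its separate bullet is the one tied to dosing.

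A reader might also infer that unrecorded transfusions will be read as transfusion-free, so that CR and HI-E are wrongly scored at every off-treatment assessment. The documents do not support that. No text treats a blank transfusion record as independence. Response and HI are assessed by the investigator (6.5.1, 6.5.2), and subjects still followed for response attend the site every 28 days, so the investigator can ask or check the chart. The unit example rests on an assumed rate, and at 6 units per 8 weeks it falls short of the threshold at the nominal first marrow. What remains is an unsupported criterion, not a demonstrated misclassification.

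**Conclusion.** The inconsistency is real and is in the current text: two collection windows, no statement of which governs follow-up, and a prompt that cannot trigger once dosing stops. Where a site follows 6.3, the SAP 8.5 follow-up summary is incomplete. No recorded transfusion data then support the CR criterion at follow-up marrows from about day 35. The same may be true in part of the HI-E count at the nominal first marrow and wholly from day 84, subject to reconciling the on-treatment wording in Appendix G with off-treatment HI assessment in 6.3.

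The size is modest. Exposure is limited to a first CR, CRi/CRp, PR or HI reached off treatment and to one descriptive table. ORR is largely protected through MLFS. The day counts assume that the follow-up marrow interval runs from the last dose. How many subjects or sites are affected cannot be derived from the documents.

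**What to change.** 1. Align the transfusion clauses in Protocol 6.2.3 and 6.3 with footnote t, so that collection continues to the next AML therapy, death, loss to follow-up, withdrawal or End of Trial.
2. In 6.3 and in the Table 4 row (and its copy in SAP 17.3), add each follow-up contact as the off-treatment prompt for asking about transfusions.
3. Reconcile the on-treatment wording in the Appendix G note (SAP 17.5) with the off-treatment HI assessment in 6.3.
4. For data already collected, flag follow-up CR or HI-E assessments whose transfusion look-back was not covered, and use the flag in a sensitivity check. A rule to withhold scoring is not needed once collection is aligned.

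The cost is wording, one question at contacts already held every 28 days, and one derived flag. The prospective gain is small: the latest amendment justification reports the primary study report as final, with 15 subjects on treatment and 16 in follow-up as of 15 March 2021. The flag is therefore the more useful part for the reported results.

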## 6.4. Safety Assessment

Safety assessments, including physical examination, vital signs, ECG, hematology, serum chemistry, cardiac markers, fasting lipid panel, pregnancy testing (for FCBP subjects only), AEs, concomitant medications and procedures, and transfusions, will be performed at the frequency specified in [Table 4](#): Table of Events, or more frequently if clinically indicated. After screening, ECHO or MUGA scans, urinalysis, and coagulation testing will be performed if clinically indicated.

### 6.4.1. Adverse Events

Refer to Section [10](#) for details on AE reporting. Information about common side effects already known about AG-120, AG-221, and azacitidine can be found in the respective IBs or will be communicated between IB. Serious and unexpected events will be communicated in the form of Investigator Notifications. This information about common side effects will also be included in the subject ICF and should be discussed with the subject as needed during the study.

### 6.4.2. Urinalysis, Coagulation, Hematology, Serum Chemistry, Cardiac Markers and Fasting Lipid Panel

All samples should be sent to the central laboratory. In the event that an immediate laboratory assessment is required to acutely manage a subject, (eg, monitoring ALT increases of  $\geq 3$  x ULN; [Appendix P](#)), local laboratory tests may be used. In addition to collecting the local laboratory sample, a second sample should be collected and sent to the central laboratory.

Refer to Section [10.3](#) for information regarding abnormal laboratory values or whether test results constitute an AE.

## 6.5. Efficacy

### 6.5.1. Response

Bone marrow aspirate (or biopsy if adequate aspirate is not attainable) samples will be collected for assessing response. The site must ensure peripheral blood for central hematology is collected and sent at the time of every bone marrow collection. As specified in the Table of Events, [Table 4](#), the frequency is within 7 days prior to study treatment administration on Cycles 2, 3 and every 2nd cycle thereafter (eg, Cycles 5, 7, 9, etc), and if clinically indicated (eg, confirmation of CR/CRi/CRp, morphologic relapse after CR/CRi/CRp or progression as defined in modified IWG AML response criteria ([Cheson, 2003](#)) ([Appendix F](#)) and International Working Group response criteria in myelodysplasia ([Cheson, 2006](#)) by a repeated bone marrow assessment at least 1 month later) or required for toxicity assessment. A bone marrow biopsy can be collected in conjunction with an aspirate if it is standard institutional practice or if clinical indicated (eg, evaluation of bone marrow cellularity). Whenever a bone marrow sample is collected, a peripheral blood smear is to be prepared. In addition, whenever a bone marrow aspirate is obtained for confirming CR/CRi/CRp, morphologic relapse after CR/CRi/CRp or progression, a

standard cytogenetic metaPhase preparation will be prepared and sent to the local laboratory for cytogenetic analysis. A bone marrow biopsy can be used for cytogenetics testing if adequate aspirate is not attainable.

Bone marrow aspirate and/or biopsy and peripheral blood smear collected after the start of study treatment must be available for both local and central pathology review. The retrospective central pathology review will require a set of duplicate slides for each bone marrow collection time point including BMA, peripheral blood smear, and BMB if performed. The central pathology review will be conducted by personnel blinded to study treatment.

Response to treatment and HI will be assessed by the investigators according to modified IWG AML Response Criteria (Cheson, 2003) (Appendix F) and IWG myelodysplastic syndromes HI criteria (Cheson, 2006) (Appendix G), respectively.

Instructions for submission slides of bone marrow aspirate (and/or biopsy) and peripheral blood smear for central pathology review are provided in the Study Reference and Study Central Laboratory Manuals.

